
Measurements

Work capacity, as measured by peak oxygen uptake with a graded exercise test on a treadmill, is the primary outcome variable. For the participants with Down syndrome, all measurements will be carried out pre- and post training under the same conditions and at the same time of day, for the control group without Down syndrome all measurements will be carried out as baseline measurements only.

Visit 1 for all participants

Baseline measures

Participants will be tested in a postprandial state (>3 h) on 2 separate days and will refrain from exercise 24 h before each test day. Participants will be also asked to refrain from drinking or eating caffeine and drinking alcohol on testing days. Participants who do not follow the requirements on study days will be

asked to come back another day. During the first visit, the participants will complete questionnaires about risk of falling (Short Falls Efficacy Scale-1), perform a cognitive function test on a laptop specifically designed for individuals with Down syndrome evaluating the following domains: Multitasking, Episodic memory, Executive function and Processing speed (Cambridge Neuropsychological Test Automated Battery (CANTAB)). After that, height, weight and circumferences will be measured. Body composition will be determined with a DEXA scan, to determine forearm composition and mass. Vascular health (arterial stiffness and central blood pressure) will be measured with the Complior Analyse device. Two-dimensional echocardiography (Hitachi Arietta 70 system, Tokyo, Japan) will be used to measure aortic root diameter, cardiac output, and stroke volume and end systolic volume at rest. In addition, clinical autonomic function tests (heart rate variability at rest and recovery after exercise, deep breathing, Valsalva maneuver, isometric exercise, active and passive orthostasis) will be evaluated during the first study visit. At the end of the first visit, all participants will be provided with an Actigraph and instructions to wear this device for 7 days.

Visit 2 for individuals with Down syndrome (added to visit 1 for individuals without Down syndrome)

Graded exercise test treadmill

Procedures

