The participants will be familiarized with the graded maximal test protocol on the treadmill. The graded maximal exercise test begins with a submaximal horizontal walk on a motorized treadmill at a individualized comfortable speed, using a validated and reliable protocol for this population [3, 4]. Grade will be increased 2.5% every 2 min until a 12.5% grade will be reached. From this point, grade will be held constant whereas speed will be increased by 0.5 mph every minute until exhaustion. This may involve running at the later stages. The exercise test will be terminated when the participant can no longer keep up with the treadmill speed or shows signs of volitional fatigue. Heart rate, blood pressure and oxygen uptake (VO₂) will be monitored continuously throughout the exercise and recovery [5]. The highest VO₂ will be recorded as VO_{2peak} if the respiratory exchange ratio is over 1.0 [6].

Measurements

Cardiac output will be measured using ultrasonography, by measuring the aortic diameter at the level of the valve form the peristernal long axis. Ascending aortic blood flow will be measured using continuous Doppler echocardiography using a pedoff probe in the suprasternal notch as we have previously described [7].

Gait and balance test protocol

This is a 30-min protocol evaluating different aspects of gait and balance with valid and reliable, easy, participant-friendly, quick and functional tests. For the Foot Posture Index the participant stands and the test instructor evaluates different aspects. This will be evaluated with and without the supportive footwear. The Timed Up and Go test is a timed test where the participant stands up from a chair, walk 10ft, turn around, walk back and sit down again, as fast as possible. For the Stair Climb test the participant is timed when climbing up a flight of 9 stairs. After that the participant performs a Functional Reach Test in the Virtubalance system, which electronically records how far the participant can reach

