Part 2B: The vasodilatory response to dynamic hand grip exercise (2 sec rest, 1 sec squeeze for 4 minutes) at 15% and 30% of the participant's MVC (with 5 min of rest in between the different intensities) will be investigated. The change in diameters and blood flow of the brachial artery will be measured in the exercising arm with Doppler ultrasound in the last 30 sec of each condition.

Part 2C: The ability to vasodilate will be further challenged by adding a mild lower body negative pressure (LBNP) of -20 mmHg and performing the same dynamic hand grip exercise protocol and measurements as described in Part 2B. All measurements will be repeated during the last 30 seconds of the LBNP application. LBNP will be stopped if systolic blood pressure drops below 80 mmHg or if participants exhibit symptoms of pre-syncope. However, this protocol has been well tolerated in our pilot studies for participants both with and without Down syndrome.

Measurements hand grip exercise protocol

Forearm blood flow and vascular conductance will be measured in both the exercising and non-exercising arm using high definition ultrasound (Arietta 70, Aloka-Hitachi). The brachial artery will be imaged in dual mode allowing for simultaneous determination of artery diameter (B-mode) and flow velocity (Doppler mode). Blood flow will be determined from the following formula: Forearm Blood flow = (Mean blood velocity) x (Brachial Cross Sectional Area) x (60) and expressed as ml/min. Forearm vascular conductance will be determined by dividing forearm blood flow by mean arterial pressure. Forearm blood flow and vascular conductance will be normalized to forearm lean mass to account for differences in lean mass between individuals.

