Descriptive statistics will be used to present baseline characteristics. A independent t-test will be used to test for differences in the change from pre to post between the exercise group and the control group. Additionally, a two-way mixed ANOVA will be used to evaluate condition (exercise and control) by time (pre-post) effects of the exercise program on the outcome measures. The a priori alpha level is set at 0.05.

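### The two planned tests are one complete-pair change test, which neither adjusts efficiently for baseline nor uses participants with one value; a constrained-baseline mixed model does both, with a modest gain that rests on assumed rates

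*Combined protocol and SAP*

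**What the plan says.** The Statistical Analysis section is the whole analysis plan. After descriptive statistics it states: "A independent t-test will be used to test for differences in the change from pre to post between the exercise group and the control group". It then adds that "a two-way mixed ANOVA will be used to evaluate condition (exercise and control) by time (pre-post) effects", with alpha at 0.05. It names no analysis population, no rule for missing values and no likelihood-based model.

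The Measurements section fixes the primary outcome: "Work capacity, as measured by peak oxygen uptake with a graded exercise test on a treadmill, is the primary outcome variable". Participants with Down syndrome are measured once before and once after the 12 weeks.

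Two rules elsewhere can leave a value missing:

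- Graded exercise test treadmill, Procedures: the highest oxygen uptake "will be recorded as VO_{2peak} if the respiratory exchange ratio is over 1.0". The text does not say what is analysed when the ratio is not reached. The Intervention paragraph makes post-intervention collection identical to baseline collection, so the rule applies at both times.
- Hand grip exercise protocol, Part 2C: "LBNP will be stopped if systolic blood pressure drops below 80 mmHg", or on symptoms of pre-syncope. The readings are due in the last 30 seconds of the pressure application, so stopping early can cut them short. The same paragraph says that the procedure was well tolerated in pilot work.

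The time of randomisation is given in two ways. The opening paragraph on data collection visits puts it directly after consent. The paragraph headed The second visit puts it at the end of the third visit.

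**The concern.** A change score needs both of its values. The ANOVA looks like a second analysis that might use more of the data, but with two time points its interaction term is the change-score test again. A participant with a valid treadmill test on only one occasion therefore contributes nothing to either. The plan does not say this in words; it follows from the methods named.

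It is often said that with one post measurement a mixed model adds little to baseline-adjusted analysis of complete pairs. That is true when every baseline is observed. Here a baseline can also be voided, and a participant with only a post value still informs the difference between arms after training. What is at stake is precision on the primary and secondary outcomes, and an analysis that leaves out some of those randomised.

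**Working it through.** **Inputs.** From the documents: two arms, one pre and one post measurement, and the two named tests. They give no sample size, standard deviation, pre-post correlation or missingness rate, so there is no planned figure to reproduce. Assumed: correlation r from 0.5 to 0.8 (0.9 as a further check), a proportion m of 10% or 20% missing at each test, independently, and unit variance at both times.

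**Step 1: are the two tests the same?** In one simulated data set with 20 per arm, the ANOVA interaction F and the square of the change-score t were both 4.4803 (p = 0.0409 for both). After one participant's post value was deleted, the ANOVA gave F = 4.1537 on 37 residual degrees of freedom. That equals t² with the participant removed altogether. The remaining baseline value added nothing.

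**Step 2: how many participants are affected?** Complete pairs are (1 − m)², and participants with exactly one value are 2m(1 − m).

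- m = 10%: 0.9² = 81% pairs; 2 × 0.1 × 0.9 = 18% with one value.
- m = 20%: 0.8² = 64% pairs; 2 × 0.2 × 0.8 = 32% with one value.

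**Step 3: information per randomised participant (large-sample).**

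- Planned change test: (1 − m)² / [2(1 − r)]
- ANCOVA on complete pairs: (1 − m)² / (1 − r²)
- Mixed model with common baseline mean: the ANCOVA term plus m(1 − m) from post-only participants

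The ratio of the second to the first is 2/(1 + r), whatever m is: 2/1.5 = 1.33 at r = 0.5 and 2/1.8 = 1.11 at r = 0.8.

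| m | r | Change test | ANCOVA, pairs | Mixed model | Mixed vs ANCOVA | Mixed vs change |
|---|---|---|---|---|---|---|
| 10% | 0.5 | 0.81/1.00 = 0.810 | 0.81/0.75 = 1.080 | 1.080 + 0.09 = 1.170 | +8% | +44% |
| 10% | 0.8 | 0.81/0.40 = 2.025 | 0.81/0.36 = 2.250 | 2.250 + 0.09 = 2.340 | +4% | +16% |
| 20% | 0.5 | 0.64/1.00 = 0.640 | 0.64/0.75 = 0.853 | 0.853 + 0.16 = 1.013 | +19% | +58% |
| 20% | 0.8 | 0.64/0.40 = 1.600 | 0.64/0.36 = 1.778 | 1.778 + 0.16 = 1.938 | +9% | +21% |

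At r = 0.9, baseline adjustment adds about 5%, and keeping half-observed participants adds 2% (m = 10%) to 5% (m = 20%).

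**Step 4: the same on the standard-error scale.** With an assumed 20 per arm, m = 20% and r = 0.7, the standard error is √[2/(20 × information)]. The information values are 1.067, 1.255 and 1.415, which give 0.306 for the change test, 0.282 for ANCOVA on pairs and 0.266 for the mixed model, in SD units. Simulation gave 0.302, 0.278 and 0.267.

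**Step 5: two limits on the gain.** If baseline is always observed and only post values are missing, there are no post-only participants. The added term is then zero and the mixed model has exactly the precision of ANCOVA on pairs. If baseline means are left free by arm, the gain over the planned test falls to 1-6% at m = 10% and 3-13% at m = 20% (r from 0.9 to 0.5).

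**The case against.** **Missing baselines may be rare.** The protocol provides familiarisation for the treadmill and the pressure chamber, extra sessions if needed, and a return visit for those who did not follow the pre-test requirements. One of its two statements on randomisation places it after the baseline visits, and it reports good tolerance of the pressure procedure. This stands as a limit on size. It does not remove the mechanism: nothing says that a participant whose baseline test misses the ratio criterion is retested or excluded.

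**Much of the gain is baseline adjustment.** This also stands. The 21-58% over the planned test at 20% missing includes 11-33% that ANCOVA on pairs would deliver. Only the remaining 9-19% comes from keeping half-observed participants.

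**A reader might infer that discarding incomplete pairs biases the result.** The documents do not support that. They give no missingness pattern, and a constructed example points to a different cause. Suppose exercise-arm post values are missing more often at low baseline (about 23%), control values are missing at random (20%) and all baselines are observed. The change test was then biased by -0.11 SD at r = 0.5 and -0.07 at r = 0.7. ANCOVA on complete pairs and the mixed model both gave 0.00. ANCOVA drops the same participants, so the bias comes from not adjusting for baseline.

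**A reader might also infer that the mixed model needs the weaker assumption.** It does not; neither assumption contains the other. Suppose exercise-arm post values are missing according to a stable personal trait, such as the ability to push past the ratio criterion. The trait cancels in the change score, but an observed baseline measures it only imperfectly. In simulation, with 20% of baselines also missing at random, the bias was 0.01 SD (change test) against 0.10 SD (mixed model) at r = 0.5, 0.00 against 0.08 at r = 0.7, and 0.00 against 0.06 at r = 0.8. That mechanism is plausible for this rule.

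**Conclusion.** The point holds as one of precision and completeness. The plan names one complete-pair change test twice, makes inefficient use of baseline, and discards participants with one value, although its own treadmill rule can void either primary value. Under the assumed rates and correlations (0.8 to 0.5), baseline adjustment is worth 11-33% more information. Retaining half-observed participants is worth a further 4-8% at 10% missing or 9-19% at 20%. At a correlation of 0.9 both gains are small, and the second is zero if only post values are missing.

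It is not a finding that the planned result would be biased, nor that the alternative is safer against every kind of missingness. Participants with neither value still contribute nothing under any of these methods.

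**What to change.** In the Statistical Analysis section, replace the two-way mixed ANOVA with a linear mixed model:

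- fitted by REML with an unstructured 2×2 covariance and small-sample degrees of freedom;
- using all observed pre and post values of all randomised participants with Down syndrome, in their assigned arm;
- with one common baseline mean, and the exercise-by-post coefficient as the effect.

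Keep the t-test on change in complete pairs as a sensitivity analysis, and say that the mixed model is the main analysis, since the two can now differ. State what is analysed when a treadmill test does not meet the ratio criterion, and report the number of missing values by arm and time point. Reconcile the two statements on the time of randomisation: the common baseline mean is most secure when baseline testing precedes allocation.

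The cost is a change of wording and a little programming, with no new data. The downside is reliance on missing at random given the observed value. That assumption differs from the change test's and is not weaker, which is why the two results should be shown side by side.

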forward. After that the participant will be timed walking over a 30ft distance at a comfortable pace to determine Gait Speed (average of 3 attempts), and then will be walking that distance at his/her fastest walking pace, to determine Fast Walking Speed (average of 3 attempts). The participants will be executing these walking bouts on the GaitMat to evaluate spatial and temporal gait parameters and they will be recorded with 2D camera to determine lower extremity kinematics (knee and hip flexion, knee valgus/varus). To conclude, the participant will perform several standing balance tasks (Bertec Balance Measures) on a force platform. We will use a harness for safety, and the participant will be asked to lean in different directions following a target on a screen (evaluating the limits of stability), to maintain position while the platform moves in different directions (evaluating motor control) and to stand still for 3x 20 seconds with eyes open and 3x 20 seconds with eyes closed (evaluation sensory organization).

Visit 3 for individuals with Down syndrome (visit 2 for individuals without Down syndrome)

Hand grip exercise protocol

Procedures

Participants will be placed in a supine position with his/her lower body in the LBNP chamber, sealed at the waist. They will be instrumented with a 3 lead ECG to measure heart rate continuously and beat-to-beat blood pressure will be measured using finger plethysmography (Finapres NOVA, TNO Biomedical Instrumentation, The Netherlands).

Resting measurements will be conducted following a 10 min supine rest period. After the resting measurements, the participants are asked to squeeze the hand grip dynamometer with maximal force. This is repeated three times in total, with 1 minute of recovery in between. The highest is used as the participant's maximal voluntary contraction (MVC). Then the different parts of the hand grip exercise protocols start, with randomization of the order of Part 2B and 2C.

Part 2A: Diameters, blood flow and vascular conductance in the brachial artery will be measured in response to a short, single contraction of hand grip exercise with a hand grip dynamometer of 1 sec, at 15% and 30% of the participant's MVC. The peak blood flow within the first 4-6 cardiac cycles following the contraction will be used to determine the immediate contraction-induced vasodilation. These measures will be performed in triplicate, with 1 minutes of rest in between.

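### The plan includes no test of whether training changes the forearm flow response to LBNP, and does not say how the four hand grip cells per visit enter the analysis

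*Combined protocol and SAP*

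**What the plan says.** The Statistical Analysis section is one short paragraph. It plans an independent t-test to "test for differences in the change from pre to post between the exercise group and the control group", and adds that "a two-way mixed ANOVA will be used to evaluate condition (exercise and control) by time (pre-post) effects". The ANOVA is directed at "effects of the exercise program on the outcome measures", which are not listed there. The only error-rate statement is "The a priori alpha level is set at 0.05".

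The data are richer than those two factors. Part 2B is dynamic hand grip at 15% and 30% MVC. Part 2C repeats the same exercise and measurements under LBNP, and its purpose is stated: "The ability to vasodilate will be further challenged by adding a mild lower body negative pressure (LBNP) of -20 mmHg". The Procedures paragraph of the hand grip protocol describes the session "with randomization of the order of Part 2B and 2C". The Measurements section says that for participants with Down syndrome "all measurements will be carried out pre- and post training under the same conditions". Each of them therefore contributes four dynamic hand grip cells (two LBNP states by two intensities) at each of two times.

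The section on hand grip measurements defines forearm flow, vascular conductance and their scaling to lean mass. It defines no variable for the response to LBNP.

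**The concern.** Part 2C exists to be set against Part 2B: same person, same exercise, with an added sympathetic challenge. Aim 1 asks whether training improves peripheral or central blood flow regulation. One natural peripheral question is whether training changes what LBNP does to flow or conductance during exercise. That is the condition-by-time-by-LBNP effect, and no planned test is named for it.

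The plan also leaves open how the cells enter the analysis: as four separate outcomes, as an average, or as a difference. These answer different questions and have different power. If the choice is made after the data are seen, a reader of the results cannot tell which forearm flow finding was the intended one. Four separate tests at 0.05 would also raise the chance of a false positive, and no multiplicity rule is given.

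**Working it through.** The documents give no sample size, standard deviation, effect size or power, so there is no stated figure to reproduce. Group size, effect and correlations below are assumptions.

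**1. What the planned methods can test.** The check used simulated data with an assumed 15 per arm and the design 2 arms × 2 times × 2 LBNP states × 2 intensities.
- Outcome = one LBNP cell: the arm-by-time F from the two-way mixed ANOVA is 2.2144, and t² from the t-test on change is 2.2144 (p = 0.148 for both). The two planned analyses are the same test, and they do test the training effect under LBNP.
- Outcome = 2C minus 2B, averaged over intensity: the arm-by-time F is 0.3622 on 1 and 28 df. The arm × time × LBNP interaction from the full three-way layout is also 0.3622 on 1 and 28 df. The missing test is the planned ANOVA applied to a derived outcome that the plan does not define.

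**2. Four cells tested separately at 0.05.** If independent, family-wise error = 1 − 0.95⁴ = 0.185. By simulation at equal correlations of 0.3, 0.5, 0.7 and 0.9 it is about 0.17, 0.16, 0.13 and 0.09.

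**3. Does the choice of outcome matter?** Suppose the effect is 0.8 SD of change, present only under LBNP, with 15 per arm. Let ρ be the correlation between the 2B and 2C changes, each with SD 1. Normal approximation: power = Φ(δ / (σ√(2/15)) − 1.96), with √(2/15) = 0.365.

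| Outcome | δ | σ | Power at ρ = 0.3 | 0.5 | 0.7 |
|---|---|---|---|---|---|
| LBNP cell | 0.8 | 1 | 0.59 | 0.59 | 0.59 |
| 2C minus 2B | 0.8 | √(2(1−ρ)) | 0.46 | 0.59 | 0.81 |
| Mean of 2B and 2C | 0.4 | √((1+ρ)/2) | 0.27 | 0.24 | 0.22 |

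For example, the difference at ρ = 0.7 has σ = √0.6 = 0.775, and 0.8 / (0.775 × 0.365) − 1.96 = 0.87, so Φ = 0.81. The difference equals the single cell when 2(1−ρ) = 1, that is, at ρ = 0.5. If training instead raises flow equally with and without LBNP, the difference has expectation zero and only the mean shows the effect. Both summaries are needed.

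**4. Is a mixed model with a random intercept alone a safe substitute?** Take post values only, residual variance 0.5² = 0.25, and participants whose LBNP response varies with SD s. The LBNP contrast averaged over two intensities has variance 0.25 + s². A random-intercept model pools it with two other within-person contrasts of variance 0.25, so its error term is about 0.25 + s²/3. The variance is understated by the ratio R = (0.25 + s²)/(0.25 + s²/3), and the true two-sided error is about 2Φ(−1.96/√R).
- s = 0.25: R = 0.3125/0.2708 = 1.15, error about 7%
- s = 0.5: R = 0.50/0.333 = 1.50, error about 11%
- s = 0.75: R = 0.8125/0.4375 = 1.86, error about 15%

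Null simulation with 15 per arm agrees, and the difference-score test stays at about 5%.

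**The case against.** The strongest reply is that nothing in the stated methods is wrong. Because the ANOVA names only condition and time, a reader might infer that it cannot test the training effect on vasodilation under LBNP. That does not follow. Applied to the Part 2C value it tests exactly that, and applied to 2C minus 2B it is the three-way interaction. What is missing is an outcome definition and a named contrast.

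A reader might also infer that the LBNP effect will be judged by seeing which cells reach significance. The plan never says so. Nor does it say that four cells will be analysed separately; an average or a difference would fit its wording equally well. The family-wise figures are therefore conditional on one possible reading.

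A third tempting inference is that arm × LBNP is the one proper test for Aim 1. The aim is broader: it covers central as well as peripheral regulation, and does not single out the LBNP response. A uniform rise in exercising flow would count as a peripheral improvement.

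Finally, a difference score is not always more precise. Below a correlation of about 0.5 it is less precise than a single cell.

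All of this stands. It narrows the point but does not remove it: no test of the LBNP response is planned, and the handling of the four cells is open.

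**Conclusion.** The point holds as a gap in specification. The plan collects a crossed within-person LBNP-by-intensity design at two times, and states analyses that work within each condition. It plans no test of whether training changes the LBNP-induced alteration in flow or conductance.

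The size depends on assumptions. Separate cell tests would carry a family-wise error of about 0.09 to 0.185 for correlations from 0.9 down to zero. In the illustration with 15 per arm and an effect of 0.8 SD under LBNP only, power runs from 0.22 to 0.81 according to the outcome and correlation.

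The change should be made, because these data bear on the first-listed aim and the repair is cheap. It is not critical: peak oxygen uptake is the primary outcome and is untouched.

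**What to change.** Add one paragraph to the Statistical Analysis section. For forearm flow and for conductance, define two outcomes per visit, each averaged over 15% and 30% MVC:
1. the mean of Parts 2B and 2C, for the overall training effect;
2. Part 2C minus Part 2B, for the LBNP response.

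Compare the post value of each between the exercise and usual-care arms, adjusting for its own baseline value. Report the individual cells as descriptive. Do not name arm × LBNP as the only Aim 1 test.

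If a mixed model is preferred, include participant-by-LBNP random effects and a term for the 2B/2C order, not a random intercept alone. The protocol foresees that LBNP may be stopped early, so the paragraph should also say how a visit without complete 2C values is handled.

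The cost is the paragraph itself, with no new data or procedures. The one statistical price is the lower precision of the difference score if the within-person correlation proves to be below about 0.5.
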